This document describes the statistical analyses for selepressin (FE202158) 000133 planned after the trial was stopped for futility, but before the blind was broken. It is an addendum to version 9.0 of the statistical analysis plan.

1.1 Abbreviations

Abbreviations Meaning of abbreviations in document

IMP Investigational medicinal product

P&VFDs Vasopressor- and mechanical ventilator-free days

Page 6 of 9

2 Post-futility / Pre-unblinding Planned Analyses

2.1 Primary Endpoint

To explore whether there was a 'learning curve' effect of administering the drug, the primary analysis will be conducted without the first 3 patients at each site.

Due to trial logistics (e.g. preparation time for pharmacy etc.) or safety concerns, some patients may receive norepinephrine instead of the investigational medicinal product (IMP) during parts of the treatment period where they have a vasopressor need. To try to mimic the 'near perfect' conditions, where IMP is used as the primary vasopressor, the primary analysis will be conducted on a subset of the per-protocol analysis set in which patients who did not have norepinephrine weaned before IMP (unless due to death), or patients in which IMP was not restarted within 6 hours upon restart of norepinephrine, will be excluded.

To evaluate the new septic shock criteria (1), the primary endpoint will be evaluated for patients with lactate ≤ 2 mmol/L at baseline (sepsis) and patients with lactate ≥ 2 mmol/L (septic shock), respectively.

The VASST trial identified a potential survival benefit using vasopressin as compared to norepinephrine in patients with less severe septic shock defined as a baseline norepinephrine dose of less than 15 μ g/min. Similarly, to assess whether there was a potential benefit of selepressin in vasopressor- and mechanical ventilator-free days (P&VFDs) in patients with less severe septic shock, the treatment effect of the primary endpoint will be presented graphically, in order to visually inspect whether the average treatment effect is distributed evenly across the baseline norepinephrine levels (\leq 15 μ g/min, >15 μ g/min).

To further assess if baseline norepinephrine impacts the treatment effect, the same analysis will be repeated for baseline norepinephrine levels ($\leq 0.1 \mu g/kg/min$,]0.1; 0.20 $\mu g/kg/min$],]0.2; 0.30 $\mu g/kg/min$],]0.3; 0.45 $\mu g/kg/min$],]0.45; 0.60 $\mu g/kg/min$], >0.60 $\mu g/kg/min$).

To assess if there is a treatment duration effect, patients will be stratified by cumulative duration of IMP infusion (<1 day, [1; 3 days[, \ge 7 days], and the treatment effect of the primary endpoint will be presented graphically, in order to visually inspect whether the average treatment effect is distributed evenly across the duration of treatment with IMP.

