2.2 Organ Dysfunction

2.2.1 Mechanical Ventilator-free Days up to Day 30

To assess if there is an effect of baseline lung function on the potential treatment effect of selepressin on lung function, the treatment effect of mechanical ventilator-free days will be presented graphically, in order to visually inspect whether the average treatment effect is distributed evenly across baseline PaO_2/F_iO_2 levels (<100mmHg, [100; 200 mmHg[, [200; 300 mmHg[, \geq 300 mmHg).

2.2.2 Duration of Mechanical Ventilation up to Day 30

The graphical presentation in section 2.2.1 will be repeated for duration of mechanical ventilation.

Page 7 of 9

2.2.3 Renal Replacement Therapy (RRT)-free Days up to Day 30 (excluding patients on RRT for chronic renal failure at time of randomisation)

RRT-free days will also be evaluated using the new septic shock definition (1) as for the primary endpoint.

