2.3 Morbidity/Mortality

2.3.1 Intensive Care Unit (ICU)-free Days up to Day 30

ICU-free days will also be evaluated using the new septic shock definition as for the primary endpoint.

2.3.2 All-cause Mortality (Defined as the Fraction of Patients That Have Died, Regardless of Cause, by the end of Day 30, Day 90, and Day 180)

Mortality will also be evaluated using both the new septic shock definition, and the baseline norepinephrine cut-offs as for the primary endpoint.

2.4 Daily and Cumulative Urinary Output Until ICU Discharge (for a Maximum of 7 Days)

Urinary output and cumulative urinary output analyses will be repeated for the two components that make up total output volume; spontaneous urine output and output fluids collected from drainages, suction devices and respiratory fluid loss estimation (if transpiration was performed).

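### The addendum's two lactate subgroups overlap: a baseline lactate of exactly 2 mmol/L falls in both the sepsis and the septic shock group

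*SAP*

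**What the plan says.** The addendum sets out analyses planned after the trial stopped for futility but before the blind was broken. To apply a newer consensus definition of septic shock, section 2.1 evaluates the primary endpoint (P&VFDs) in "patients with lactate ≤ 2 mmol/L at baseline (sepsis) and patients with lactate ≥ 2 mmol/L (septic shock), respectively".

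Three later sections reuse that split by reference instead of restating it:

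- Section 2.2.3: "RRT-free days will also be evaluated using the new septic shock definition (1) as for the primary endpoint".
- Section 2.3.1: "ICU-free days will also be evaluated using the new septic shock definition as for the primary endpoint".
- Section 2.3.2, for mortality at Days 30, 90 and 180: "Mortality will also be evaluated using both the new septic shock definition, and the baseline norepinephrine cut-offs as for the primary endpoint".

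Section 2.1 also contains a separate severity split by baseline norepinephrine. It recalls an earlier vasopressin trial that reported a possible survival benefit in "less severe septic shock defined as a baseline norepinephrine dose of less than 15" µg/min. It then plans a plot to see whether "the average treatment effect is distributed evenly across the baseline norepinephrine levels", with strata of at most 15 and above 15 µg/min.

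**The concern.** The two lactate groups are labelled as different conditions, sepsis and septic shock, and are meant to be read side by side. As written, both include the boundary. A patient recorded at exactly 2 mmol/L is therefore in both groups, the group sizes add up to more than the number of patients with a lactate value, and the two estimates share patients.

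The split reaches four sets of endpoints: P&VFDs, RRT-free days, ICU-free days and mortality. RRT-free days, ICU-free days and Day 90 mortality are the three key secondary endpoints in SAP section 2.2.2.

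The addendum's purpose is to fix these analyses while the data are still blinded. An unresolved boundary leaves a small choice that could be made after the results are known.

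**Working it through.** No sample size, power or alpha figure is involved, and the plan states no count to reproduce. The check is one of set membership.

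**Inputs**, all from addendum 2.1:

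- lactate groups: L ≤ 2 (sepsis) and L ≥ 2 (septic shock);
- norepinephrine strata: D ≤ 15 and D > 15 µg/min;
- weight-adjusted norepinephrine bands in µg/kg/min: ≤ 0.1, above 0.1 to 0.20, above 0.2 to 0.30, above 0.3 to 0.45, above 0.45 to 0.60, and > 0.60.

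The recording grids are assumptions: lactate 0.5 to 10.0 mmol/L in steps of 0.1, dose 4.5 to 40 µg/min in steps of 0.5, and weight-adjusted dose in steps of 0.01. The results at the boundaries do not depend on them.

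**Lactate**

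| Rule | Values in both groups | Values in neither |
|---|---|---|
| ≤ 2 and ≥ 2 (as written) | 2.0 | none |
| ≤ 2 and > 2 | none | none |
| < 2 and ≥ 2 | none | none |

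Let N be the number of patients with a baseline lactate and n₂ the number at exactly 2 mmol/L. As written, the two group sizes sum to N + n₂. With either strict inequality they sum to N. The document gives neither n₂ nor the precision to which lactate is recorded, so the excess cannot be given a value.

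**Norepinephrine**

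The strata ≤ 15 and > 15 µg/min give no overlap and no gap. The lower stratum contains one grid value, 15.0, that the earlier trial's boundary of below 15 would exclude. The weight-adjusted bands place every value in exactly one band, and each bounded band is closed on the right, as is the ≤ 15 stratum.

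**Comparison with the rest of the plan**

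Other cut-offs are written without overlap. SAP 9.2.1 uses < or ≥ 6 hours and < or ≥ 30 µg/min, SAP 9.3.1.7 adds creatinine < or ≥ 150 µmol/L, and addendum 2.2.1 uses half-open PaO₂/FiO₂ bands. The lactate overlap therefore looks like a slip, not a deliberate choice.

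**The case against.** **The sign may be an extraction error.** The whole defect is one character, ≥ instead of >, in text extracted from a PDF, and that extraction does damage such items. The strata table in Appendix 7 shows norepinephrine cut-offs with altered signs and digits, and the IMP-duration bands in addendum 2.1 end with an unmatched bracket. On the other side, addendum 2.1 renders > correctly for 15 µg/min and for 0.60 µg/kg/min. The objection stands far enough that the original page should be checked first.

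**The harm is limited.** Each lactate group is still a comparison of randomised arms within a subgroup defined at baseline, and sharing one boundary value does not bias either comparison. A reader might infer that a contrast between the two groups would be blunted, but the addendum specifies no such contrast or interaction test. The analyses also lie outside the primary test (SAP 9.2.1) and the Hochberg procedure (SAP 9.3). This stands in full.

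**The norepinephrine strata.** A reader might infer that these contradict the addendum's own definition at exactly 15 µg/min. The document does not support that. The below-15 boundary is attributed to the earlier trial. The sentence that follows, "Similarly, to assess whether there was a potential benefit of selepressin in vasopressor- and mechanical ventilator-free days (P&VFDs) in patients with less severe septic shock", carries over the question but does not say that the identical cut is adopted. The addendum's own strata are disjoint and exhaustive and match the right-closed bands in the next paragraph. What remains is a difference from the earlier trial's boundary at a single value, in a plot meant for visual inspection.

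**Conclusion.** The lactate overlap holds as a minor specification error. On the text as it stands, exactly 2 mmol/L belongs to both groups, and the error passes by reference to RRT-free days, ICU-free days and mortality. This assumes only that the printed sign is ≥.

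The number of patients affected cannot be computed. It is tempting to apply an assumed share at the boundary to the planned 1800 patients, but the document supports no such share, and 1800 was the planned total of a trial that stopped for futility.

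Nor does the document support reading this as a threat to the trial's conclusions. The effect is confined to exploratory subgroup analyses added after the futility stop. The document also does not settle on which side the boundary value belongs: either strict inequality cures the overlap.

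**What to change.** 1. Check the second lactate inequality in addendum 2.1 against the original page. If it reads > there, nothing needs to change.
2. If it reads ≥, make one of the two inequalities strict before unblinding, for example ≤ 2 and > 2 mmol/L. The sponsor should choose the side from the consensus definition that the addendum cites.
3. Leave sections 2.2.3, 2.3.1 and 2.3.2 as they are, since they take the split from section 2.1 by reference.
4. Leave the norepinephrine strata unchanged. At most, add a note that their boundary differs from the earlier trial's at exactly 15 µg/min.

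The cost is one character in the addendum. No data, sample size or primary analysis is touched.

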9.2 Primary Endpoint

• Vasopressor- and mechanical ventilator-free days (P&VFDs) up to day 30

This composite endpoint is defined as the number of days (reported to one decimal place (0.0 to 30.0)) from start of treatment with the investigational medicinal product (IMP) [selepressin or placebo] to 30.0 days thereafter during which the patient is: 1) alive; 2) free of treatment with intravenous vasopressors; and 3) free of any invasive mechanical ventilation (see definition below).

Patient Death

By definition, any patient that dies within this 30-day period will be assigned zero P&VFDs, even if there is a period during which the patient is alive and free of both vasopressor treatment and mechanical ventilation.

Definition of "Free of Vasopressors"

Free of vasopressors means less than 60 minutes during any contiguous 24-hour period (regardless of calendar day). If a patient requires periods of vasopressors longer than 60 minutes in total during any 24-hour period, the intervening intervals during which they are free of vasopressors will not be included in the period free of vasopressors in the determination of the number of P&VFDs. Thus, the period free of vasopressors begins at the end of the last use of vasopressors that was either: 1) longer than 60 minutes in duration; or 2) part of greater than 60 minutes of use within a contiguous 24-hour period.

Norepinephrine/noradrenaline, phenylephrine, dopamine, epinephrine/adrenaline, vasopressin, terlipressin, and IMP (i.e. selepressin and placebo) all constitute a vasopressor for the purpose of the primary analysis.

Vasopressor use due to anaesthesia or procedure-induced hypotension during and up to three hours after a surgery or procedure (including bedside) is exempt from this rule (i.e. such use of vasopressors would not affect the calculation of P&VFDs).

Date: 20 Nov 2017 E-Statistical Analysis Plan-17877; Ver.9.0 Supersedes: Ver. 8.0

Page 24 of 80

Definition of "Free of Mechanical Ventilation"

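### The addendum's plot of the primary effect by realised IMP duration, and its 'near perfect' weaning subset, both select patients after randomisation; the plot misleads if selepressin changes vasopressor time, the subset if exclusions differ by arm

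*SAP*

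**What the plan says.** The addendum's introduction describes its analyses as "planned after the trial was stopped for futility, but before the blind was broken". Two items in its Section 2.1 matter here.

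- **Duration display.** For the primary endpoint, "patients will be stratified by cumulative duration of IMP infusion", and the effect is plotted "in order to visually inspect whether the average treatment effect is distributed evenly across the duration of treatment with IMP". The printed classes are under 1 day, 1 to under 3 days, and 7 days or more. No 3-7 day class is printed, possibly because text was lost in extraction.
- **'Near perfect' subset.** The primary analysis is repeated within the per-protocol set after two further exclusions. The first removes "patients who did not have norepinephrine weaned before IMP (unless due to death"). The second states that "patients in which IMP was not restarted within 6 hours upon restart of norepinephrine, will be excluded".

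SAP Section 9.2 defines the endpoint. Among the listed agents, "IMP (i.e. selepressin and placebo) all constitute a vasopressor for the purpose of the primary analysis". It also states that "any patient that dies within this 30-day period will be assigned zero P&VFDs". Under Section 9.2.1 the primary analysis is a stratified van Elteren test at the two-sided 5% level, accompanied by effect estimates.

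**The concern.** Cumulative IMP duration becomes known only after treatment starts, and it enters the endpoint directly. Brief and procedural use aside, a patient with 7 or more days of IMP cannot score above 30 - 7 = 23 P&VFDs. Death stops infusion and sets the score to zero, so early deaths fall into the short strata whatever their severity. If selepressin shortens vasopressor need, patients move to shorter strata in the active arm only. A stratum then holds different kinds of patients in the two arms, and randomisation does not protect the comparison.

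The subset raises a related problem. Weaning order and IMP restart also arise after randomisation. SAP Section 9.4.5 itself compares norepinephrine weaning between arms as an outcome, and Addendum Section 2.1 gives safety concerns as one reason for using norepinephrine in place of IMP. Exclusion could therefore differ by arm.

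After a futility stop, results like these may be used to argue that the drug works for some treatment durations or under ideal use. A false gradient, or a p-value from groups that are not comparable, could feed that argument.

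**Working it through.** **Design anchor.** SAP Appendix 8 assumes 25% placebo mortality and a mean of 24 P&VFDs in survivors, so 0.75 × 24 = 18 overall. With the Section 3.2 effect (1.5 points lower mortality, 1.5 more days in survivors), 0.765 × 25.5 - 18 = 1.51. This reproduces the stated 1.5 days.

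**How patients move.** Take a survivor with no ventilation beyond the shock period and 8 days of IMP on placebo: 30 - 8 = 22 P&VFDs. If the drug shortens support by 25%, IMP lasts 8 × 0.75 = 6 days and the score is 24. The gain is 2 days, but the patient has left the longest stratum for the next one, in the active arm only.

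**Simulation of the plot.** Three million patients were simulated with both potential outcomes, calibrated to 25% mortality and 24 days in placebo survivors. The following are assumptions, not in the documents:

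- lognormal shock times;
- a severity factor shared by shock, ventilation and death;
- IMP duration equal to shock duration, cut at death;
- a 3-7 day class.

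The drug multiplies shock and ventilation times by 0.75 and lowers mortality from 25.0% to 23.7%, an overall effect of 1.36 days. True effects group patients by the IMP duration they would have had on placebo. Displayed effects group them by observed duration.

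| IMP days | Placebo share | Active share | True effect | Displayed effect |
|---|---|---|---|---|
| <1 | 18.1% | 25.5% | +0.73 | +2.14 |
| 1 to <3 | 40.3% | 43.5% | +1.10 | +0.23 |
| 3 to <7 | 28.9% | 23.4% | +1.67 | -0.05 |
| ≥7 | 12.6% | 7.6% | +2.35 | +0.17 |

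The rising gradient becomes one in which the shortest stratum looks best. Other assumptions give:

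- Another set with the same overall effect of 1.36 days: true 1.04, 1.18, 1.49, 2.59; displayed 1.34, 0.65, 0.46, 0.58.
- First model, IMP time not cut at death: true 0.58, 1.13, 1.68, 1.95; displayed -0.11, -0.23, -0.36, +0.04. Here the plot hides the effect rather than putting the peak in the shortest stratum.
- IMP time lengthened by 25%, overall effect -0.36: true -0.05, -0.18, -0.46, -1.16; displayed -1.90, +0.50, +0.97, +0.55.
- No effect: displayed effects are within 0.01 of zero.
- Ventilation only: true 0.37, 0.65, 0.86, 0.68; displayed 0.38, 0.65, 0.87, 0.68. No bias beyond simulation error.

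**Subset by hand.** Assume no true effect, the Appendix 8 placebo figures in both arms, and exclusion of a fraction f of survivors whose mean is m days. The mean of those kept is (18 - 0.75·f·m) / (1 - 0.75·f). Take f = 0.20 on selepressin and 0.10 on placebo (assumed).

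- m = 12: 16.2/0.85 - 17.1/0.925 = 19.06 - 18.49 = +0.57 days.
- m = 22: 14.7/0.85 - 16.35/0.925 = 17.29 - 17.68 = -0.38 days.
- m = 18: both means are 18, so no bias.

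The sign depends on which survivors are excluded and in which arm exclusion is more common. Equal rates with the same m give no bias.

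**The case against.** Neither analysis decides anything. Section 9.2.1 rests trial success on the pooled primary comparison, the duration item is a plot with no test, and the subset is introduced as an attempt to mimic ideal use. Both were fixed before unblinding. All of this stands and limits the consequence to interpretation. A reader might infer that the primary test or its type I error is compromised; the documents do not support that.

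The bias is also conditional. With no effect, or one that leaves IMP time unchanged, the plot is sound, and a trial stopped for futility may be close to that case. This too stands. But a change in vasopressor time is one way the drug could work on the primary endpoint, and in that case the plot cannot be trusted.

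Four further readings go too far:

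- The plot does not turn an effect that is equal in days into a false gradient in the cases shown. The shortening is uniform only as a proportion, and the true effects in days already rise with duration.
- Gradient reversal cannot apply to the subset, which yields a single estimate.
- The subset does not clearly keep all deaths. The exemption is attached to the weaning criterion, for failures due to death, and not clearly to the restart criterion.
- Dependence of weaning order on response to the drug is an inference. The addendum names logistics as well as safety concerns.

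Finally, strata of predicted duration answer a different question, namely heterogeneity by baseline. That is true, but it is a question that a randomised comparison can answer.

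**Conclusion.** The point holds in conditional form. The duration plot stratifies on a post-randomisation component of the outcome. If selepressin changes vasopressor time, the plot can show a false, flattened or reversed gradient. In the calibrated example the displayed effects differ from the true ones by +1.41 days in the shortest stratum (2.14 - 0.73) and -2.18 days in the longest (0.17 - 2.35), against a design effect of 1.5 days. Those sizes depend on the assumed severity links, the handling of IMP time at death and the assumed 3-7 day class; only the mechanism follows from the SAP's own definitions.

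The subset estimate and p-value are biased if exclusion differs by arm among patients whose outcomes differ from the average. The direction cannot be fixed in advance; about +0.6 to -0.4 days is an illustration under assumed rates. The addendum carries no caveat on either analysis. Its lactate, norepinephrine-dose and PaO2/FiO2 subgroups use baseline variables and do not share the problem.

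**What to change.** Replace the realised-duration strata with strata of IMP duration predicted from baseline variables. Fit the model to placebo patients only and apply it to both arms, as SAP Section 9.2.2 already does for the risk of dying. Otherwise drop the plot. Print the full set of duration classes if any are kept.

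Report the 'near perfect' subset descriptively, with the number excluded by arm and by reason. Label it as selected after randomisation and not a causal comparison, and omit the van Elteren p-value. State whether the death exemption also covers the restart criterion.

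The cost is a change to the addendum's wording, one extra prediction model and the loss of a simple plot. No data collection and no part of the primary analysis changes.

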2.2 Organ Dysfunction

2.2.1 Mechanical Ventilator-free Days up to Day 30

To assess if there is an effect of baseline lung function on the potential treatment effect of selepressin on lung function, the treatment effect of mechanical ventilator-free days will be presented graphically, in order to visually inspect whether the average treatment effect is distributed evenly across baseline PaO_2/F_iO_2 levels (<100mmHg, [100; 200 mmHg[, [200; 300 mmHg[, \geq 300 mmHg).

2.2.2 Duration of Mechanical Ventilation up to Day 30

The graphical presentation in section 2.2.1 will be repeated for duration of mechanical ventilation.

Page 7 of 9

2.2.3 Renal Replacement Therapy (RRT)-free Days up to Day 30 (excluding patients on RRT for chronic renal failure at time of randomisation)

RRT-free days will also be evaluated using the new septic shock definition (1) as for the primary endpoint.

2.3 Morbidity/Mortality

2.3.1 Intensive Care Unit (ICU)-free Days up to Day 30

ICU-free days will also be evaluated using the new septic shock definition as for the primary endpoint.

2.3.2 All-cause Mortality (Defined as the Fraction of Patients That Have Died, Regardless of Cause, by the end of Day 30, Day 90, and Day 180)

Mortality will also be evaluated using both the new septic shock definition, and the baseline norepinephrine cut-offs as for the primary endpoint.

2.4 Daily and Cumulative Urinary Output Until ICU Discharge (for a Maximum of 7 Days)

Urinary output and cumulative urinary output analyses will be repeated for the two components that make up total output volume; spontaneous urine output and output fluids collected from drainages, suction devices and respiratory fluid loss estimation (if transpiration was performed).

